## 1 INTRODUCTION

This document describes the statistical methods and data presentations to be used in summarizing and analyzing the safety, tolerability, and efficacy data from Protocol ASN002-101. Background information is provided for the overall study design and objectives. The reader is referred to the study protocol and case report forms (CRFs) for details of study conduct and data collection.

Pharmacokinetic analyses and reporting are not included in this analysis plan.

## 2 STUDY OBJECTIVE(S), TREATMENTS, AND ENDPOINT(S)

### 2.1 Study Objectives

#### 2.1.1 Primary Objectives

The primary objectives of this study are:

Part A:

- To evaluate the safety and tolerability of ASN002 including dose-limiting toxicities (DLTs) and to determine the maximum tolerated dose (MTD).

Part B:

- To evaluate the safety, tolerability, and preliminary efficacy of ASN002 in subjects with relapsed/refractory diffuse large B-cell lymphoma (DLBCL), follicular lymphoma (FL), mantle cell lymphoma (MCL), peripheral T-cell lymphoma (PTCL), myelofibrosis (MF), and chronic lymphocytic leukemia (CLL).

#### 2.1.2 Secondary Objectives

Part A and B:

- To evaluate the pharmacokinetic (PK) profile of ASN002 after single and multiple doses.

#### 2.1.3 Exploratory/Pharmacodynamic Objectives

Parts A and B:

- To evaluate the effects of ASN002 on Phospho-STAT3, Phospho-S6, Phospho-SYK 525/526, Phospho-ERK, and a panel of markers of inflammation (Appendix C of Protocol Amend 6).
- Evaluate the response to therapy based on DLBCL molecular subtype [germinal center B-cell like (GCB) or activated B-cell (ACB)].
- To evaluate the effects of ASN002 on JAK (V617F) mutant allele burden in subjects with MF.
- To evaluate the effects of ASN002 on BCL2, and chromosome 17p.

### 2.2 Treatment Comparisons

The dose escalation component (Part A) of this study will identify – based on safety and tolerability – a dose of ASN002 to be evaluated within the cohort expansion component of the study (Part B). In Part B, eligible subjects will enroll into one of the six disease-specific cohorts (DLBCL, FL, MCL, PTCL, MF and CLL) and receive the dose of ASN002 identified in Part A.

## **2.3 Study Endpoints and Evaluations**

### **2.3.1 Efficacy**

#### **2.3.1.1 Primary Efficacy Variable**

The primary efficacy variable for this study is disease response to ASN002. It is expected that the investigator will choose the most appropriate method for radiographic assessment of the individual subject's disease status. Subjects with a diagnosis of lymphoma are expected to undergo CT (for non-FDG-avid lymphoma), or PET-CT (for FDG-avid lymphoma) for their efficacy evaluation. Subjects with advanced or metastatic solid tumors are expected to undergo CT with contrast (unless medically contraindicated) or MRI for their efficacy evaluation.

For patients with MF spleen measurement will be performed by palpation and by MRI (preferred) or CT scan.

For patients with CLL a baseline CT scan of chest/abdomen/pelvis and a bone marrow aspirate and biopsy are desirable.

If Part B is not completed, only listings will be generated for descriptive summary of efficacy.

#### **DLBCL, MCL, FL, and PTCL**

The International Conference on Malignant Lymphoma (ICML) Recommendations for Initial Evaluation, Staging, and Response Assessment of Hodgkin and Non-Hodgkin Lymphoma (2014 Lugano Classification) will be used to determine the stage of subjects with lymphoma, and the response to treatment.

For cohorts that have at least 5 subjects at the recommended Part B dose of 75 mg BID, the following endpoints will be used to determine the response to treatment with ASN002 in subjects with lymphomas:

- Objective Response Rate
- Duration of Response
- Time to Tumor Progression (TTP)
- Progression-free Survival (PFS)
- PFS rate at week 24

For cohorts with less than 5 subjects at the recommended Part B dose of 75 mg BID, efficacy will be summarized in a descriptive manner for those subjects who have at least stable disease per protocol criteria.

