## 4 SAMPLE SIZE CONSIDERATIONS

### Part A:

A traditional 3+3 design will be used to identify the MTD. In addition to the 40 subjects enrolled in the previous amendments, an additional 24 subjects may be enrolled and dose in either fed or fasted states. A total of 64 subjects will be enrolled into the Part A dose escalation phase of the study. No randomization will be performed for Part A.

Part B: A sample size of 84 subjects (14 each in DLBCL, MCL, FL, PTCL, MF, and CLL) will be enrolled. The null hypothesis that the true response rate is 0.05 will be tested against a one-sided alternative. A total of 14 patients will be accrued in each cohort. The null hypothesis will be rejected if at least 3 responses are observed in 14 subjects. This design yields a type I error rate of 0.02 and power of 0.9 when the true response rate is 0.4.

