## **9.1 Evaluation of Disease Status**

### **9.1.1 DLBCL, MCL, FL, PTCL**

For cohorts that have at least 5 subjects at the recommended Part B dose of 75 mg BID, the frequency of responders according to the 2014 Lugano Classification for subjects with lymphoma will be evaluated at each dose level and for each lymphoma subgroup in Part B. Differences in response to therapy based on the molecular subtypes of DLBCL will be explored.

Assessments will be made after every two 28-day cycles of therapy, i.e., starting just before Day 1 of cycle 3 and then just before each odd-numbered cycle, for solid tumor patients and after every 3 cycles, i.e., just before Day 1 of cycle 4 and then just before cycles 7, 10, and 13, etc, for lymphoma patients.

In Part B, response to treatment will be analyzed using the binomial test for each of the disease-specific cohorts (DLBCL, MCL, FL, PTCL, MF and CLL). The dichotomous classifications to be assessed in each binomial test are disease responders versus non-responders. Responders will be considered as subjects with 2014 Lugano Classifications given by Complete Response (CR) or Partial Response (PR), and non-responders as subjects with 2014 Lugano Classifications given by No Response (NR) or Stable Disease (SD), or Progressive Disease (PD). For each binomial test, the null hypothesis is that the rate of disease responders is 5% and the one-sided alternative hypothesis is that the rate of disease responders is greater than 5%. The null hypothesis will be rejected if the p-value is less than 0.05 (i.e., using a one-sided significance level of 0.05).

Summaries for best disease response will be provided by treatment cohort for subjects diagnosed with lymphoma using frequencies (counts and percentages). For Part B, the estimated rate of disease responder and the p-value from the binomial test will be provided by disease-specific cohort (DLBCL, MCL, FL, PTCL, MF and CLL).

Response to treatment will be provided in a data listing by subject.

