### **12 INTERIM ANALYSIS**

An interim analysis is not applicable to this study. As this is an open-label study, appropriate analyses will be conducted on an ongoing basis.

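### SAP 9.1.1 sets no minimum size for the binomial response test, so Part B cohorts of 5 to 13 can be tested under a critical value and power that SAP 4 does not give

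*SAP*

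**What the plan says.** SAP section 4 describes a single Part B design. On size: "A total of 14 patients will be accrued in each cohort". On the decision: "The null hypothesis will be rejected if at least 3 responses are observed in 14 subjects". On its properties: "This design yields a type I error rate of 0.02 and power of 0.9 when the true response rate is 0.4". Protocol 15.1 says the same.

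SAP 9.1.1 holds the analysis: "In Part B, response to treatment will be analyzed using the binomial test for each of the disease-specific cohorts". Its decision rule is "The null hypothesis will be rejected if the p-value is less than 0.05", one-sided. Neither sentence names a cohort size or a number of responses. The section begins with "For cohorts that have at least 5 subjects at the recommended Part B dose of 75 mg BID", where the condition is attached to the frequency of responders. SAP 2.3.1.1 uses the same threshold to decide when response rate, duration of response, TTP and PFS are used as endpoints.

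Three other places bear on how many subjects are tested:

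- SAP 3.1 makes 14 the upper limit of a cohort, not a fixed size.
- SAP 5.3 makes the per-protocol population primary for efficacy, so the analysed number can be below the number enrolled.
- SAP 9 falls back to listings only when no indication has completed Part B. One completed cohort is therefore enough to open efficacy analysis for all of them.

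**The concern.** A rule written as a p-value applies at any cohort size, but the number of responses it demands changes with that size. Two responders among 7 would be declared positive and two among 8 would not, and the SAP does not tell the reader so. A non-rejection in a cohort of 8 would be read against a printed power of 0.9 that does not belong to it.

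Disease response is the primary efficacy variable (SAP 2.3.1.1), and Protocol 6.4.1 says the Part B data will inform later development decisions. What counts as a positive or negative cohort should be known before the data are seen, at every size at which a test is allowed.

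**Working it through.** **Inputs.** SAP 4 gives the null rate, 0.05 ("The null hypothesis that the true response rate is 0.05 will be tested against a one-sided alternative"), the cohort size 14, the critical value 3, the alternative rate 0.40, and the stated alpha 0.02 and power 0.9. SAP 9.1.1 gives the one-sided cut-off p < 0.05, and SAP 6.5 the same level.

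**Formula.** For n subjects, critical value r and true rate p, the exact rejection probability is T(n, r, p) = 1 − Σ C(n,k) p^k (1−p)^(n−k), summed over k = 0 to r−1. Alpha is T(n, r, 0.05) and power is T(n, r, 0.40).

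**Step 1: the plan's own figures.**

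- Alpha, 3 of 14: 1 − 0.4877 − 0.3593 − 0.1229 = 0.030.
- Power, 3 of 14: 1 − 0.0008 − 0.0073 − 0.0317 = 0.960.

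The stated 0.02 and 0.9 are not reproduced. Three of 12 would fit that pair (0.0196 and 0.917). The documents do not explain the difference.

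**Step 2: do the two rules agree at 14?** Two of 14 gives p = 0.153 and three of 14 gives p = 0.030. At n = 14, p < 0.05 therefore means 3 or more responses, which is the SAP 4 rule.

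**Step 3: smaller cohorts.** For each n, take the smallest r with T(n, r, 0.05) < 0.05.

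- n = 5, r = 2: alpha = 1 − 0.7738 − 0.2036 = 0.023. Power = 1 − 0.0778 − 0.2592 = 0.663.
- n = 8: two responses give p = 0.057, so three are needed.

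| Analysed n | Responses to reject | Alpha | Power at 40% |
|---|---|---|---|
| 5 | 2 | 0.023 | 0.66 |
| 6 | 2 | 0.033 | 0.77 |
| 7 | 2 | 0.044 | 0.84 |
| 8 | 3 | 0.006 | 0.68 |
| 9 | 3 | 0.008 | 0.77 |
| 10 | 3 | 0.012 | 0.83 |
| 11 | 3 | 0.015 | 0.88 |
| 12 | 3 | 0.020 | 0.92 |
| 13 | 3 | 0.025 | 0.94 |
| 14 | 3 | 0.030 | 0.96 |

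Power falls from 0.84 to 0.68 when an eighth subject is added, because the critical value steps up. At n = 8 the chance of missing a 40% rate is 1 − 0.68 = 0.32, against 1 − 0.96 = 0.04 in a full cohort.

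**Step 4: exact or approximate.** SAP 9.1.1 does not say which form of the binomial test is meant. With z = (r/n − 0.05) / √(0.05 × 0.95 / n) compared with 1.645, two responses would reject at every n from 5 to 13. The true type I error would then run from 0.057 at n = 8 to 0.135 at n = 13. The table holds only if the test is exact.

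**The case against.** The strongest reply is that nothing here breaks the test. A single exact test stays under the SAP's declared 0.05 at every size from 5 to 14, and in a full cohort it is the design rule itself. Two of 5 (p = 0.023) is, if anything, stronger evidence against 5% than three of 14 (p = 0.030). All of that stands.

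It is also fair that testing from 5 subjects is an inference. The threshold in SAP 9.1.1 qualifies the frequency of responders, the one in SAP 2.3.1.1 qualifies the endpoints, and the test sentence has none. SAP 2.3.1.1 also says that only listings are produced if Part B is not completed, which is stricter than SAP 9 and on a strict reading might rule out short cohorts. Protocol 8.2 counts 148 evaluable subjects and allows for 10% early termination (148 × 1.10 is about 163), so shortfall is partly provided for. These points make a small tested cohort less likely but do not exclude it: SAP 9 needs only one completed indication, and per-protocol exclusions can shrink any cohort.

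Three stronger readings are tempting, and the documents do not support them:

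- **That SAP 4 and SAP 9.1.1 contradict each other.** SAP 4 speaks only of 14 subjects. It does not say that two responses are too few in a smaller cohort.
- **That type I error is inflated above 0.05.** For one exact test it is not. It exceeds the stated 0.02 at n = 5 to 7, and also at 13 and 14.
- **That the test may be repeated as a cohort fills.** A reader might infer this from "As this is an open-label study, appropriate analyses will be conducted on an ongoing basis". The same section says an interim analysis does not apply, SAP 13 plans one final analysis after database lock, and no schedule of repeated tests appears anywhere.

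**Conclusion.** The point holds as a gap in specification. SAP 9.1.1 leaves the size at which the response test may be run open, and below 14 the SAP gives neither a critical value nor operating characteristics. At 5 to 7 subjects two responses suffice, with power 0.66 to 0.84. At 8 to 11 three are needed, with power 0.68 to 0.88. At 12 and 13 power is already 0.92 and 0.94, so those cohorts are not a problem. Separately, the printed alpha and power are wrong for the full cohort: 3 of 14 gives 0.030 and 0.960.

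This rests on an exact test performed once, on the SAP's own 40% alternative, and on reading the 5-subject threshold in SAP 9.1.1 together with the completion condition in SAP 9. The documents give no basis for how likely a cohort of 5 to 11 is. The change is cheap and worth making; it does not undermine the result of a full cohort.

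**What to change.** In SAP 9.1.1, state that the exact one-sided binomial test is run once per cohort, at the final analysis described in SAP 13, in cohorts with at least 12 analysed subjects, and that 3 or more responses reject. Count the minimum on subjects in the primary efficacy population, so that one or two exclusions from a cohort of 14 do not cancel the test. For smaller cohorts, report responders over N with an exact confidence interval and no formal rejection. If the sponsor prefers to keep the test in smaller cohorts, tabulate the critical value, alpha and power for each permitted size, as in the table above.

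In the same edit, correct SAP 4 and Protocol 15.1, and the matching text in the protocol synopsis, to alpha 0.03 and power 0.96 for 3 of 14. State that these figures apply to full cohorts.

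The cost is a few sentences. The only loss is the p-value in small incomplete cohorts.

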### **15.6.1 Evaluation of Disease Status**

#### **15.6.1.1 DLBCL, MCL, FL, PTCL**

The frequency of responders according to the 2014 Lugano Classification for subjects with lymphoma will be evaluated at each dose level and for each lymphoma subgroup in Part B. Differences in response to therapy based on the molecular subtypes of DLBCL will be explored.

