### **Myelofibrosis**

The International Working Group-Myeloproliferative Neoplasms Research and Treatment (IWG-MRT) and European LeukemiaNet (ELN) response criteria will be used to evaluate the response to treatment with ASN002. If less than 5 subjects were enrolled at the recommended Part B dose of 75 mg BID, efficacy will be summarized in a descriptive manner for those subjects who have at least stable disease per protocol criteria.

The following endpoints will be used to determine the response to treatment with ASN002 in subjects with MF:

- Splenic response rate at week 24
- Clinical improvement rate at week 24
- Symptom response evaluated using the Myeloproliferative Neoplasm Symptom Assessment Form (MPN-SAF) tool
- rate of RBC transfusion through week 24

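### In cohorts of fewer than 5 subjects the SAP describes efficacy only for subjects with at least stable disease, with no denominator, so assessed progressors fall outside the summary

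*SAP*

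**What the plan says.** SAP 2.3.1.1 splits the efficacy reporting at 5 subjects.

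- **Five or more.** For lymphoma: "For cohorts that have at least 5 subjects at the recommended Part B dose of 75 mg BID, the following endpoints will be used". The list is response rate, duration of response, time to progression, PFS and the week-24 PFS rate. Nobody is selected on outcome. In the Part B binomial test, SAP 9.1.1 counts CR and PR as response, and no response, stable disease and progression as non-response.
- **Fewer than five.** The lymphoma and solid-tumour paragraphs begin "For cohorts with less than 5 subjects at the recommended Part B dose of 75 mg BID" and continue "efficacy will be summarized in a descriptive manner for those subjects who have at least stable disease per protocol criteria". The MF and CLL paragraphs start from enrolment, "If less than 5 subjects were enrolled at the recommended Part B dose of 75 mg BID, efficacy will be summarized in a descriptive manner", and then apply the same stable-disease restriction. None of the four asks for the number treated, or for the number who progressed or were not assessed.

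The protocol has no small-cohort rule. Section 15.6.1.1 says that the frequency of responders "will be evaluated at each dose level and for each lymphoma subgroup in Part B". Sections 15.6.1.3 and 15.6.1.4 plan the frequency and type of response for MF and CLL without a filter. The synopsis promises response rate, time to progression and PFS for each lymphoma histology, MF and CLL. Protocol section 15 gives the SAP priority where the two differ, and SAP section 14 declares no changes from the protocol.

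**The concern.** Entry to the small-cohort summary depends on the result that the summary is meant to convey. A subject scanned and found to have progressed cannot appear in it, however many such subjects there are. With no denominator required, a reader of the summary alone cannot tell one controlled subject out of one from one out of four.

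Preliminary efficacy is part of the Part B primary objective, and in a cohort of 1 to 4 subjects the description is all the efficacy summary there is. Progression is not rare in this study: Protocol 6.3 reports that 13 of the 27 patients treated in Part A by the cut-off (13/27 = 48%) had stopped because of it. Some of those may have had stable disease first, so 48% is not the share that the filter would remove, but the filter acts on a common outcome.

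**Working it through.** The documents give no figure for cohorts under 5, so there is nothing to reproduce. The check compares the two rules and then illustrates the size.

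**Same subject, two cohort sizes.** Take an assessed subject whose best result is progression.

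| Cohort at 75 mg BID | Treatment of this subject | Source |
|---|---|---|
| 5 or more | Counted as a non-responder in the denominator | SAP 9.1.1 |
| 1 to 4 | Outside the descriptive summary, and not counted beside it | SAP 2.3.1.1 |
| Any size | Included, no filter | Protocol 15.6.1.1, 15.6.1.3, 15.6.1.4 |

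**Worked cohort.** Four treated subjects, all assessed, 1 with stable disease and 3 with progression.

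- SAP rule: 1 subject is described, and that subject has disease control.
- All treated: 1/4 = 25%. The exact (Clopper-Pearson) 95% limits are the 2.5% quantile of Beta(1, 4), which is 1 − 0.975^(1/4) = 0.006, and the 97.5% quantile of Beta(2, 3), which is 0.806. The interval is 0.6% to 80.6%.
- With 2 of 4 at stable disease or better, all treated gives 50% (6.8% to 93.2%). The SAP rule again describes only controlled subjects.

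**How often this arises.** Let p be the true chance of stable disease or better. The documents give no value, so p is assumed over a range. Take n = 4, all assessed and independent.

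- Nobody qualifies, summary empty: (1 − p)^4
- At least one qualifies: 1 − (1 − p)^4
- At least one qualifies and at least one is left out: 1 − p^4 − (1 − p)^4

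| Assumed p | Empty | At least one qualifies | Qualifies, but someone left out |
|---|---|---|---|
| 20% | 0.41 | 0.59 | 0.59 |
| 30% | 0.24 | 0.76 | 0.75 |
| 50% | 0.06 | 0.94 | 0.88 |

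Whenever the summary is not empty, everyone in it has disease control by construction. For a single-subject cohort at p = 30%, the summary is empty with probability 1 − 0.30 = 0.70.

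**Response among those described.** If a reader formed a response rate from the subjects described, its expected size would be about the true response rate divided by p. An assumed true rate of 20% would read as 0.20/0.40 = 50%, 0.20/0.50 = 40% or 0.20/0.70 = 29%.

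**The case against.** **The data are not hidden.** SAP 6.6 lists all collected data, and SAP 9.1.1 adds "Response to treatment will be provided in a data listing by subject". SAP 8.2 tabulates reasons for discontinuation on the Safety Population, and Protocol 9.3 names progression and death among those reasons. SAP 10.1 lists deaths and subjects who dropped out for adverse events before a tumour assessment. This stands: a reader might infer that progressors disappear from the report, and they do not. But a listing elsewhere does not repair a summary that selects on outcome. Two possible remedies are also uncertain. The unfiltered best-response table in SAP 9.1.1 sits in a section that opens with the at-least-5 condition. The disposition tables are by treatment cohort, which the SAP's definitions spell out only as Part A dose levels.

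**The SAP plans no disease-control rate below 5 subjects.** True. The 100% figure is what the described group shows, not a statistic that the plan asks for. The omission of the other subjects from the description remains.

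**The rule will seldom apply.** SAP 2.3.1.1 sends efficacy to listings if Part B is not completed, and SAP section 9 does so if it is not completed for at least one indication. Solid-tumour efficacy already goes to listings and ranges under section 9. This narrows the scope. What is left is mainly one indication completing while another enrols 1 to 4 subjects; section 9, read as requiring just one completed indication, does not replace the filter then.

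**Unassessed subjects are lost anyway.** Also true. The efficacy and per-protocol populations (SAP 5.2, 5.3) require an evaluable post-dose assessment at any cohort size, so that loss is not particular to this rule. What the rule adds is the removal of assessed progressors.

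**The SAP has priority over the protocol.** It does, and for that reason the filter would govern. Priority does not make SAP section 14 accurate.

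**Conclusion.** The point holds, within limits. Below 5 subjects the SAP's efficacy summary is selected on outcome and carries no denominator. It treats progressors differently from larger cohorts and departs from the protocol without saying so. In a 4-subject cohort with 1 stable and 3 progressing, it describes 1 controlled subject where the full account is 1 of 4. At assumed rates of 20% to 50% for stable disease or better, 59% to 88% of 4-subject cohorts would yield a non-empty summary that leaves someone out. These percentages rest on the assumed rates and on all four subjects being assessed; the selection itself rests on neither.

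Two stronger inferences are not supported. A reader might conclude that every small cohort will appear to benefit, but a cohort with nobody at stable disease or better has an empty summary (41%, 24% or 6% of 4-subject cohorts at 20%, 30% or 50%). A reader might also argue that the filter cannot apply to MF because none of the four listed MF endpoints has a stable-disease level. The clause points to the protocol's response criteria, which for MF are the IWG-MRT/ELN criteria. The documents do not reproduce these, so the question cannot be settled here.

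The rule does not touch the 3-of-14 decision rule, the binomial test or the safety analyses. It should be corrected before analysis, but it does not threaten the design.

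**What to change.** In each of the four disease paragraphs of SAP 2.3.1.1, replace the restriction to subjects with at least stable disease by wording such as: *for all treated subjects in the cohort, giving the number treated and the count in each best-response category, including PD and not evaluable/not assessed (or the category under the applicable MF or CLL criteria)*. Record the small-cohort rule in SAP section 14 as a change from the protocol.

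The cost is SAP wording, since the data are already collected and listed. There are two consequences to accept. The description may look less favourable. Small cohorts would also be described on all treated subjects while larger ones stay on the per-protocol and efficacy populations; the SAP should state that difference so that the two are not read side by side as like for like.
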